## 12.2.2 Immediately Reportable Events

Immediately Reportable Events (IREs) are events that must be reported immediately to MacroGenics within 24 hours of the study site’s awareness of the event.

- SAEs
- Pregnancy in a study patient or partner of a study patient. [Note: If the female partner of a male patient becomes pregnant, the partner must be requested to complete a Pregnant Partner Consent Form so that pregnant partner, fetal and/or newborn information can be collected.] Upon confirmation of serum pregnancy testing, the patient will be followed for the outcome of pregnancy. All live newborns will be followed 6 months after the birth, and all necessary information will be collected to assess the effects of study drug on the newborn. If necessary, the follow-up period will be extended for the newborn.
- The following AESIs ([Section 12.2.4](#)):
  - $\geq$  Grade 3 IRRs or CRS
  - Grade 2 or greater immune-related AEs of the following: events of colitis, pneumonitis, hepatitis, Stevens-Johnson syndrome (SJS), and toxic epidermal necrolysis (TEN), myocarditis, nephritis, hypophysitis, and hypo/hyper-thyroidism which are considered immune-mediated events
  - Abnormal liver enzymes that meet the criteria for potential Hy’s law, which is defined as AST and/or ALT that is greater than  $3 \times$  ULN and total bilirubin that is greater than  $2 \times$  ULN and without any alternate etiology
  - Grade 2 or greater diarrhea associated with visible blood in the stool or melena
  - Any Grade 3 or greater diarrhea irrespective of evidence of GI bleeding
- Administration of a dose significantly greater (specifically, + 20% or higher) than the planned dose, and results in an event of clinical consequence.

- AEs leading to permanent discontinuation of study drug in an individual patient.
- Withdrawal of the patient from study drug administration for any reason other than disease progression.

In those cases, in which the IRE is considered related to study drug, the study drug may be discontinued, and the patient will continue participation in the study for observational safety and analysis (except for cases where the patient is withdrawn from the study by the Investigator or withdrew the consent). At any time after completion of the study, if an Investigator becomes aware of a serious adverse event that s/he suspects is related to study drug, the Investigator should report the event to MacroGenics Product Safety.

### **12.2.3 Serious Adverse Events**

All SAEs occurring during the study must be reported to the Sponsor.

After 30 days following the last dose of study drug administration, only SAEs the Investigator believes considered related to study drug or a protocol procedure, should be reported to the Sponsor.

Information regarding SAEs will be transmitted to the Sponsor using the Serious Adverse Event Form, which must be completed and signed by a physician from the study site and transmitted to the Sponsor within 24 hours of the site becoming aware of the serious adverse event. The initial and follow-up serious adverse reports should be scanned and emailed or transmitted by facsimile (fax) to the Sponsor.

All Grade 3 or Grade 4 SAEs considered related to study drug must be followed until recovery to baseline or Grade 1.

The Investigator must follow all SAEs until resolution and record the date of resolution. Resolution of an event is defined as the return to pre-treatment status or stabilization of the condition with the expectation that it will remain chronic.

All SAEs that have not resolved by the end of the study, or that have not resolved upon discontinuation of the patient's participation in the study, must be followed until any of the following occurs:

- The event resolves.
- The event stabilizes.
- The event returns to baseline, if a baseline value/status is available.

- The event can be attributed to etiology other than the study drug or to factors unrelated to study conduct.
- It becomes unlikely that any additional information can be obtained (patient or health care practitioner refusal to provide additional information, lost to follow-up after demonstration of due diligence with follow-up efforts).

Any event requiring hospitalization (or prolongation of hospitalization) that occurs during the course of a patient's participation in a study must be reported as a SAE, except hospitalizations for the following:

- A standard hospitalization for administration of study drug therapy will not be reported as a serious adverse event.
- A procedure for protocol/disease-related investigations (e.g., surgery, scans, endoscopy, sampling for laboratory tests, bone marrow sampling, pharmacokinetic or biomarker blood sampling).
- Hospitalizations not intended to treat an acute illness or adverse event (e.g., social reasons such as pending placement in long-term care or hospice facility).
- Surgery or procedure planned before entry into the study (must be documented in the eCRF).

Disease progression should not be recorded as an AE or SAE term; events related to disease progression/worsening of underlying disease (including those with a fatal outcome) will be collected as efficacy endpoints and not documented as AEs/SAEs. These events may not qualify for expedited reporting to regulatory agencies if consistent with expected rates of progression for the underlying disease. However, if an SAE occurs in a patient and it is unclear if the event is due to progressive disease, the SAE should be reported.

#### **12.2.4 Protocol-specific Adverse Events of Special Interest**

Specific adverse events or groups of adverse events will be followed as part of standard safety monitoring activities by the Sponsor. The Sponsor will be notified of these events in a timely manner, regardless of seriousness (i.e., serious and non-serious adverse events).

- All infusion-related reactions or CRS events (Note:  $\geq$  Grade 3 IRRs or CRS events are additionally considered immediately reportable events) (see [Section 7.2](#))
- Grade 2 or greater Immune related AEs of the following: events of colitis, pneumonitis, hepatitis, Stevens-Johnson syndrome (SJS), and toxic epidermal necrolysis (TEN), myocarditis, nephritis, hypophysitis, and hypo/hyper-thyroidism which are considered immune-mediated events (see [Section 7.5](#))

- Abnormal liver enzymes that meet the criteria for potential Hy's law, which is defined as AST and/or ALT that is greater than  $3 \times$  ULN and total bilirubin that is greater than  $2 \times$  ULN and without any alternate etiology
- Grade 2 or greater diarrhea associated with visible blood in the stool or melena
- Any Grade 3 or greater diarrhea irrespective of evidence of GI bleeding

### 12.2.5 Pregnancy

All initial reports of pregnancy in female patients or partners of male patients must be reported to the Sponsor by the study-site personnel within 24 hours of their knowledge of the event using the MacroGenics Pregnancy Exposure Form. Abnormal pregnancy outcomes (e.g., spontaneous abortion, fetal death, stillbirth, congenital anomalies, ectopic pregnancy) are considered SAEs and must be reported using the Serious Adverse Event Form. Any patient who becomes pregnant during the study must discontinue further study drug administration.

Because the effect of the study drug on sperm is unknown, pregnancies in partners of male patients included in the study will be reported by the study-site personnel within 24 hours of their knowledge of the event. If the female partner of a male patient becomes pregnant, the partner must be requested to complete a Pregnant Partner Consent Form so that pregnant partner, fetal and/or newborn information can be collected.

Upon confirmation of serum pregnancy testing, the patient will be followed for the outcome of pregnancy. All live newborns will be followed at birth and 6 months after birth, and all necessary information will be collected to assess the effects of study drug on the newborn. If necessary, the follow-up period will be extended for the newborn.

### 12.2.6 Reporting of Adverse Events to the Sponsor

Throughout the study, the Investigator must document all AEs on the eCRF in a timely manner. IREs, as defined in [Section 12.2.2](#) are events that must be reported immediately to MacroGenics within 24 hours of being identified. These IREs must be transmitted via an SAE form (if the event meets serious criteria) or be entered into the eCRFs within 24 hours of awareness; see [Table 9](#).

The Investigator must immediately complete and transmit the Serious Adverse Event (SAE) Report Form, within 24 hours of identifying the serious adverse event, to MacroGenics Product Safety or designee. The SAE Report Form and Completion Guidelines, and Contact Information for Reporting SAEs, are found in the Study Procedures Manual.

For reports of pregnancy, the MacroGenics Pregnancy Exposure Form must be completed and transmitted to MacroGenics Product Safety within 24 hours of becoming aware of the pregnancy. The Investigator must attempt to follow the pregnancy to term or termination in order to report the outcome and health status of the mother and child. The Pregnancy Exposure Form is found in the Study Procedures Manual.

Please refer to the **Table 12** for reporting timeframes to MacroGenics by event type.

**Table 12 CP-MGD007-02 Safety Reporting**

Type of Event:	Hard Copy Form/Timeline for reporting/Where to Report	eCRF Timeline for Data Entry
Serious Adverse Event (SAE) *a	Serious Adverse Event Form within 24 hours of awareness Report mail to [contact] Or fax to [contact]	Within 5 calendar days of awareness
Pregnancy a	Pregnancy Exposure Form/ Within 24 hours of awareness/ Email to [contact] Or fax to [contact]	Within 5 calendar days of awareness
≥ Grade 3 IRRs or CRS b	Not Applicable*	Within 24 hours of awareness
Hy's law b (AST and/or ALT that is greater than 3 × ULN and total bilirubin that is greater than 2 × ULN, without any alternate etiology)	Not Applicable*	Within 24 hours of awareness
≥ Grade 2 immune-related AEs b	Not Applicable*	Within 24 hours of awareness
≥ Grade 2 diarrhea associated with visible blood in the stool or melena b	Not Applicable*	Within 24 hours of awareness
≥ Grade 3 diarrhea irrespective of evidence of gastrointestinal bleeding b	Not Applicable*	Within 24 hours of awareness
AEs leading to permanent discontinuation of study drug in a patient b	Not Applicable*	Within 24 hours of awareness
Withdrawal of patient from study drug administration due to toxicity (e.g. AE, SAE, AESI) or pregnancy b	Not Applicable*	Within 24 hours of awareness
Administration of a dose significantly greater (specifically, + 20% or higher) than the planned dose, and results in an event of clinical consequence b	Not Applicable*	Within 24 hours of awareness
Product quality issues with an associated clinical consequence b	Not Applicable*	Within 24 hours of awareness
Non-Serious Adverse Events (except for Pregnancy) c	Not Applicable	Within 5 calendar days of awareness

**Abbreviations:** AE = adverse event; AESI = adverse event of special interest; CRS = Cytokine Release Syndrome; eCRF=electronic case report form; IRR = infusion-related reaction; SAE = serious adverse event.

\*If it meets SAE criteria – refer to SAE reporting instructions

- a Hard Copy Form within 24 hours of awareness and eCRF data entry within 5 calendar days.
- b E-CRF data entry within 24 hour of awareness.
- c E-CRF data entry within 5 calendar days of awareness.

## **13 PRODUCT QUALITY COMPLAINT HANDLING**

A product quality complaint (PQC) is defined as any suspicion of a product defect related to manufacturing, labeling, or packaging, i.e., any dissatisfaction relative to the identity, quality, durability, or reliability of a product, including its labeling or package integrity. A PQC may have an impact on the safety and efficacy of the product. Timely, accurate, and complete reporting and analysis of PQC information from studies are crucial for the protection of patients, investigators, and the Sponsor, and are mandated by regulatory agencies worldwide. The sponsor has established procedures in conformity with regulatory requirements worldwide to ensure appropriate reporting of PQC information; all studies conducted by the Sponsor or its affiliates will be conducted in accordance with those procedures.

### **13.1 Procedures**

All initial clinical PQCs must be reported to the Sponsor by the study-site personnel within 24 hours after being made aware of the event.

If the defect is combined with a SAE, the study-site personnel must report the PQC to the Sponsor according to the SAE reporting timelines (refer to [Section 12.2.3](#), Serious Adverse Events). A sample of the suspected product should be maintained for further investigation if requested by the Sponsor.

### **13.2 Contacting Sponsor Regarding Product Quality**

Report any product quality issue via e-mail to the following:  
**[contact].**

## 14 STATISTICAL ANALYSIS

This section outlines the statistical methodology and principles which will be used for data analysis in this study. A separate statistical analysis plan (SAP) and statistical programming plan (SPP) will further describe the details regarding statistical methods and will govern the analysis.

### 14.1 Determination of Sample Size

The study plans to treat approximately 52 patients: up to 27 in Dose Escalation Phase and approximately 25 in the Cohort Expansion Phase.

The sample size of up to 27 patients for each cohort in the Dose Escalation Phase is based on 3+3+3 design with planned 3 dose cohorts. Additional patients may be enrolled for nonevaluable patients or if the enrollment to a dose cohort is expanded (up to 15 patients) or intermediate dose levels are evaluated in Dose Escalation Phase.

The Cohort Expansion Phase plans to treat approximately 25 patients in relapsed/refractory metastatic colorectal carcinoma, approximately 90% of them are MSS patients, e.g., 22 MSS and 3 MSI-H patients. At the end of the Cohort Expansion Phase, 15 paired tumor biopsies will be required, if tumor lesions are accessible with acceptable clinical risk (see [Section 5.1, # 9](#)). If 15 paired biopsies have not been collected in the initial 25 patients, additional patients with paired tumor biopsies will be enrolled, to ensure that the 15 paired biopsies are obtained.

The sample size in the Cohort Expansion Phase is primarily based on providing preliminary estimation of objective response rate and disease control rate. [Table 13](#) provides the 2-sided 95% confidence interval (CI) for a number of potential responses among the 25 patients.

**Table 13 Response Rates and 95% Confidence Intervals**

Sample Size	Number of Responses	Response Rate (%)	95% Confidence Interval (%)
25	2	8	1.0, 26.0
25	3	12	2.5, 31.2
25	4	16	4.5, 36.1
25	5	20	6.8, 40.7
25	6	24	9.4, 45.1
25	7	28	12.1, 49.4

During the Cohort Expansion Phase, patients who withdraw before completing the first tumor assessment for a reason other than clinically confirmed progressive disease or death may be considered unevaluable for response. In these cases, replacement patients may be enrolled in the same dose level.

## 14.2 Analysis Populations

The study analyses will be performed on the following populations:

- **Safety Population:** All patients who received at least one dose of any study drug. This population will be used for analyses of safety, PD, and immunogenicity. It will also be used for summary of baseline data and analyses of PFS and OS.
- **Response Evaluable Population:** All patients who received at least one dose of any study drug, had baseline measurable disease, and had at least one post-baseline radiographic tumor assessment or discontinued treatment due to clearly documented, clinically progressive disease or death. This population will be used for summary of tumor assessment data and analyses of response rates.

## 14.3 Demographics and Baseline Characteristics

Patient disposition, demographics, baseline characteristics, disease history, medical history, and prior cancer treatment will be summarized using descriptive statistics.

## 14.4 Study Drug Exposures and Concomitant Medications

Study drug exposures and concomitant medications will be summarized by descriptive statistics. The summary of study drug exposure will include descriptive statistics as well as frequency counts for the number of doses or cycles received, the total dose actually administered as well as the total dose intended, and the dose intensity which is calculated as percentage of total dose actually administered divided by total dose intended during whole treatment period. Dose intensity by cycle will be summarized.

## 14.5 PK/PD Analysis

### 14.5.1 Pharmacokinetic Analysis

Summary statistics will be tabulated separately for serum PK parameters by MGD007 and MGA012 dose. Geometric means and percent coefficients of variation will be reported for  $C_{\max}$ ,  $AUC_{(0-T)}$ ,  $AUC_{(TAU)}$ ,  $AUC_{(INF)}$ , and  $C_{\text{trough}}$ ; arithmetic means and standard deviations will be reported for  $t_{1/2}$ , CL, and  $V_{ss}$ ; and medians, minimum, and maximum will be reported for  $T_{\max}$ . Separate scatter plots of  $C_{\max}$  and AUC will be provided versus dose to assess dose dependency. Dose proportionality may be assessed using a power model. Population PK analyses may be conducted using data from this study alone or combined with data from other studies.

### 14.5.2 Immunogenicity Analysis

The proportion of patients who are negative for ADA at baseline and become positive in this assay, the proportion of patients who are negative at baseline and remain negative, and those who have positive ADA at baseline that increases or decreases in titer over the course of treatment will be summarized. Analysis will be conducted separately for MGD007 and MGA012.

### 14.5.3 Pharmacodynamic Analysis

Summary statistics for pharmacodynamic parameters, such as, but not limited to, those listed under in [Section 10.2](#) and corresponding changes from baseline, will be summarized and/or may also be presented graphically as will possible associations between changes in pharmacodynamic measures of interest and MGD007 in combination with MGA012 dose and exposure may be explored.

## 14.6 Efficacy and Endpoint Analyses

### 14.6.1 Response Endpoints and Analyses

For RECIST v1.1, the best overall response (BOR) will be categorized as CR, PR, SD, PD, or NE. To be qualified as BOR, CR and PR require confirmation at least 4 weeks after initial observation of such response, and SD requires to be observed at least once after 8 weeks (minus 3 days) from the start of MGD007 treatment.

For irRECIST, the best overall response (BOR) will be categorized as irCR, irPR, irSD, irPD, or irNE. To be qualified as BOR, irCR, irPR, and irPD require confirmation at least 4 weeks after initial observation of such response, and irSD requires to be observed at least once after 8 weeks (minus 3 days) from the start of MGD007 treatment.

The objective response rate (ORR) per RECIST v1.1 is estimated as the proportion of patients in response evaluable population who achieve BOR of CR or PR. Disease control rate is calculated as the proportion of patients who achieve a CR, PR, or SD. Progression-free

survival rate at 16 weeks will be calculated as the probability that patients are free of disease progression and alive at 16 weeks after the first dose of MGD007 by Kaplan-Meier method described below, based on response evaluable population and safety population, respectively. The 2-sided 95% exact binomial CI of the response rates will be calculated. The response rates per irRECIST will be estimated similarly. Subgroup analyses of these response rates by KRAS gene type (wild and mutant) and by MMR status (MSS and MSI-H) will be performed.

### 14.6.2 Analysis of Tumor Size Change Over Time

The tumor size is defined as the sum of diameters of the target lesions. The tumor size change from baseline over time will be summarized and may be presented by spider plot. The best tumor size percent change from baseline will be presented by waterfall plot.

### 14.6.3 Time-to-event Endpoints and Analyses

Progression-free survival will be defined as the time from the first dose date of MGD007 to the date of first documented progression or death from any cause, whichever occurs first. The documented progression is determined by objective assessment of disease per RECIST v1.1 and irRECIST, respectively. For patients who are not known to be dead or progressed at the time of data cut-off for PFS analysis, the PFS will be censored at the date of the last tumor assessment. Specifically, the following censoring rules will be applied as primary analysis of PFS. Sensitivity analyses may be performed to assess the robustness of the primary PFS analysis and will be described in the SAP.

**Table 14 Censoring Rules for Primary Analysis of PFS**

Situation	Date	Outcome
No baseline tumor assessments	First dose date	Censored
Death prior to first scheduled tumor assessment	Date of death	Progressed
No post-baseline tumor assessments in absence of death prior to first scheduled tumor assessment	First dose date	Censored
Documented progression	Date of progression	Progressed
Initiation of alternative anti-cancer treatments in absence of documented progression	Date of last tumor assessment prior to initiation of such treatment	Censored
Death or documented progression immediately after missing two or more consecutive scheduled tumor assessments	Date of last tumor assessment prior to missed assessments	Censored

Duration of Response (DoR) is defined as the time from the date of initial response (CR or PR) to the date of first documented progression or death from any cause, whichever occurs first. The DoR is calculated only for the responders. For responders who are not known to be

dead or progressed at the time of data cut-off for DoR analysis, the DoR will be censored at the date of the last tumor assessment. Specifically, the last three situations described in **Table 14** will be applied. The DoR analyses will be performed only if there are enough responders to render the analyses meaningful.

Overall survival (OS) is defined as the time from the first dose date of MGD007 to the date of death from any cause. For patients who are not known to be dead at the time of data cut-off for OS analysis, the OS will be censored at the time they are last known to be alive.

The Kaplan-Meier method will be applied to estimate PFS, DoR, and OS curves; their median times; PFS rates at 4 (corresponding to 16 weeks), 6, and 12 months; and OS rates at 6, 12, and 24 months, respectively. The method of Brookmeyer and Crowley (3) will be used to construct 95% CI for median time of each time-to-event endpoint. The 95% CIs for PFS and OS rates at each time point of interests will be calculated by normal approximation after log(-log) transformation. PFS and OS will be analyzed by MMR status and by KRAS gene type when sample size warrants.

The above PFS and DoR analyses will be performed with the documented progression determined by RECIST v1.1 and irRECIST, respectively.

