## **3.2 Cohort Expansion Phase**

### **3.2.1 Primary Objective**

To investigate antitumor activity of MGD007 combined with MGA012 when dosed at the MTD (or maximum administered dose [MAD] if no MTD is defined) as measured by objective response rate, disease control rate and PFS rate at 16 weeks in patients with relapsed/refractory metastatic colorectal carcinoma using both conventional Response Evaluation Criteria in Solid Tumors (RECIST 1.1), [Appendix 5](#), and immune-related response criteria (irRECIST), [Appendix 6](#).

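### The 16-week PFS rate is set at two times that are not equal on the SAP's own scale, day 112 and day 121.75, and the first cuts through the second-scan window

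*Protocol*

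**What the plan says.** Protocol 3.2.1 defines the expansion phase's primary objective through "objective response rate, disease control rate and PFS rate at 16 weeks in patients with relapsed/refractory metastatic colorectal carcinoma", and SAP 2.2.1 repeats it. The 16-week rate is then described in two places in each document.

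- **Response sections.** In Protocol 14.6.1 the defining sentence reads, in part, "survival rate at 16 weeks will be calculated as the probability that patients are free of disease progression and alive at 16 weeks". Time runs from the initial MGD007 dose, and the method is Kaplan-Meier. SAP 6.6.1 also says 16 weeks and sends the reader to SAP 6.6.2.1 for the method.
- **Time-to-event sections.** Protocol 14.6.3 and SAP 6.6.2.1 list "PFS rates at 4 (corresponding to 16 weeks), 6, and 12 months". SAP 5.1.2 computes PFS in months as (event or censoring date − first dose date + 1) / (365.25/12).

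Appendix 1 of the Protocol schedules tumor scans at Cycle 1 Day 56 (±3 days) and every 8 weeks after that, with a Cycle 2 Day 56 (±3 days) visit.

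Two neighbouring sentences also matter. On intervals, Protocol 14.6.1 says "The 2-sided 95% exact binomial CI of the response rates will be calculated", while 14.6.3 says "The 95% CIs for PFS and OS rates at each time point of interests will be calculated by normal approximation after log(-log) transformation". On subgroups, 14.6.1 says "Subgroup analyses of these response rates by KRAS gene type (wild and mutant) and by MMR status (MSS and MSI-H) will be performed", while 14.6.3 says "PFS and OS will be analyzed by MMR status and by KRAS gene type when sample size warrants".

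**The concern.** The text treats 16 weeks and four months as the same time. On the SAP's own conversion they are almost ten days apart, and neither document fixes a day. In many trials ten days would hardly matter. Here radiographic progression is found mainly at scheduled scans, and the second scan is due at study day 112 give or take three days. A Kaplan-Meier curve drops sharply over those few days, so the choice of landmark decides which second-scan progressions count.

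Two programmers working correctly from different sections could report different values for a primary measure. The same applies to the irRECIST version, because SAP 6.6.2.1 repeats the PFS analyses for irPFS. SAP 6.1 describes the study as mainly descriptive, so what is at stake is whether the estimate can be reproduced and how it is read, not an error rate.

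**Working it through.** **Inputs.** Month length 365.25/12 = 30.4375 days and the +1 day rule (SAP 5.1.2). Treatment cycles of 8 weeks = 56 days (Protocol 4.1). Scan days and windows (Protocol Appendix 1). Expansion cohort of 25 (Protocol 14.1). The documents give no figure for how many patients progress at the second scan or how scan dates spread within the window; those are assumptions below.

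**1. The plan's own equation.** 4 × 30.4375 = 121.75 days. 16 × 7 = 112 days = 112/30.4375 = 3.68 months. The difference is 121.75 − 112 = 9.75 days. The two agree only if a month is taken as 28 days, which is not the SAP's conversion.

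**2. When the second scan falls.** Cycle 2 Day 56 is study day 56 + 56 = 112, so the window is days 109 to 115. With the first dose on day 1 and the SAP's +1 rule, study day equals PFS duration in days. The last window day is 115/30.4375 = 3.78 months, so the whole window lies before month 4.

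**3. Which on-time progressions count.**

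- Reading at day 121.75: all seven window days count.
- Reading at day 112: days 109–112 count. Progressions dated 113–115 do not, and those patients still stand as progression-free. Late share 3/7.
- Reading 16 weeks as first-dose date plus 112 days: this is 113 days under the +1 rule, so only days 114–115 are missed. Late share 2/7.

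**4. Size.** Let f be the share of the cohort whose progression is first seen at the second scan. With no censoring or other events between the two times,

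gap = f × (share of those scans that are late).

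With scan dates spread evenly over the seven days:

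| f (assumed) | 3/7 late | 2/7 late |
|---|---|---|
| 10% | 4.3 points | 2.9 points |
| 20% | 8.6 points | 5.7 points |
| 30% | 12.9 points | 8.6 points |

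The earlier landmark always gives the higher rate. If no scan is late the gap is 0; if all are late it equals f.

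**5. Assumed example with counts.** Take 25 patients, 13 still at risk at the second scan, 6 progressing there, none censored. At day 121.75 the rate is (13 − 6)/25 = 28%, whatever the scan dates. At day 112 it is 28% if none of the six scans is late, (13 − 3)/25 = 40% if three are, and 13/25 = 52% if all six are.

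**The case against.** The strongest reply is that there is only one time point. Every objective says 16 weeks, and the time-to-event sections mention four months only while equating it with 16 weeks. The exact day may also be fixed in the statistical programming plan, which SAP section 7 says will hold the programming specifications and which, with the SAP, "will further describe the details regarding statistical methods and will govern the analysis". That plan is not among the documents, so this cannot be ruled out. It is fair to call the defect an inexact equation and not two deliberately different rules. The equation is still wrong on the SAP's scale, and a primary measure's landmark belongs in the SAP.

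The size can be challenged too. It rests on assumed values of f and of scan timing, and the 2/7 reading is as literal as the 3/7 one. Protocol 4.4.1 allows interruptions of up to 28 days with visits resuming where they stopped, so scans tied to cycle days may leave the 109–115 window altogether. Both points stand as limits on the estimate.

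Stronger conclusions are tempting. A reader might infer that nothing says which section governs this rate. The documents do not support that: SAP 6.6.1 sends the method to 6.6.2.1, SAP 6.6.2.1 assigns the log(-log) interval to the 4-month PFS rate by name, and the Protocol makes the SAP govern. The interval is therefore largely settled.

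A reader might also infer that the MMR split is unconditional in one section and conditional in the other. That follows only if the PFS rate is one of the response rates meant in 14.6.1. Protocol 14.2 and SAP 4.1 list PFS analyses and response-rate analyses separately, under different populations, and SAP 6.1 ties response rates to the response evaluable population. The sentence order in 14.6.1 leaves the wording open, but a conflict is only a possible reading. The missing threshold for the conditional split is a lack of detail in a descriptive plan, not an error.

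**Conclusion.** The point holds for the landmark day. A primary expansion measure is placed at 112 days in one section and at 121.75 days in another, and the earlier time falls inside the second-scan window. Under even scan timing, with 10% to 30% of patients first progressing at that scan, the day-112 rate exceeds the day-121.75 rate by 4.3 to 12.9 points, or by 2.9 to 8.6 points if 16 weeks means first-dose date plus 112 days. It could be zero. These figures assume no censoring or other events between the two times and scans kept to schedule. The interval method and the MMR split need a clarifying sentence only. The matter is worth correcting but modest: the study is descriptive, and no error rate or objective is affected.

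**What to change.** In Protocol 14.6.1 and 14.6.3 and SAP 6.6.1 and 6.6.2.1, define the 16-week PFS rate as the Kaplan-Meier estimate at one stated study day after the second-scan window closes, counting the first dose as day 1. Day 116 would do, described as the 16-week scan plus its window; day 121.75 would do if four months is kept. Delete or correct the statement that four months corresponds to 16 weeks, and use the same day for irPFS.

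Two clarifications can go in with it: that this rate takes the log(-log) interval of SAP 6.6.2.1, and whether it is among the response rates to be split by MMR status.

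The cost is a few sentences, with no new data, visits or patients. The downside is a landmark a few days later than a nominal 16 weeks, and a rate that may be slightly lower. A fixed day removes dependence on scan timing within the allowed window, but not the effect of scans moved further by dose delays.
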